16.5.2 Patients who reduced the daily prescribed LEN dose

Incidence and frequency of TEAEs by the degree of LEN dose reduction

TEAEs will be tabulated by SOC, PT, and NCI-CTCAE Grade as described in Section 10.7 for the following subgroups of patients:

- Patients with no reduction of LEN.
- Patients with a minimum LEN dose of 20 mg/day: for this category, all TEAEs that occurred *before* exceeding the threshold of 20 mg/day are considered. The calculation of incidence rates is based on the number of patients in the SAF.
- Patients with a minimum LEN dose of <20 mg/day but ≥5mg/day: for this category, all TEAEs are considered that happened *after* exceeding the threshold of 20 mg/day. The calculation of incidence rates is based on the number of patients who had a reduction to <20 mg/day but ≥5mg/day.

Duration of TEAEs of interest

The duration of various TEAEs of interest will be summarized for the following dose categories:

- Patients who are treated with 25 mg LEN per day
- Patients who are treated with 20 or 15 or 10 or 5 mg LEN per day
- Patients who are treated with 15 or 10 or 5 mg LEN per day

For each category only those TEAEs are considered that happen *during* the period of treatment with the particular dose or dose range defining the categories above (e.g., only those TEAEs are considered that happen during while the patient is on 15 or 10 or 5 mg LEN per day). The duration of a particular TEAE is summarized for the following TEAEs:

- Neutropenia ≥G3 (PT 'neutropenia')
- Thrombocytopenia ≥G3 (PT 'thrombocytopenia')
- Infections and infestations ≥G3 (SOC 'infections and infestations')
- Infective pneumonia ≥G3 (SMQ code 20000231, narrow scope)
- Urinary tract infection ≥G3 (CMQ as defined in the SAP Appendix)

-
- Sepsis \geq G3 (CMQ as defined in the SAP Appendix)
 - Febrile neutropenia (PT 'febrile neutropenia')
 - Thromboembolic events of all CTCAE Grades (SMQ code 20000081)
 - Thromboembolic events \geq G3 (SMQ code 20000081)

16.5.3 Evaluation of the influence of different CMC batches

In L-MIND patients were treated with different production batches of the material patients were treated with (denoted with CMC2 and CMC4 material). A summary will be produced showing the number of patients who were treated with:

- CMC2 only
- CMC4 only
- Both CMC2 and CMC4 material

For those patients who were first treated with CMC2 and later with CMC4 the 'time to switch' will be displayed in a histogram. The time to switch will be summarized.

Evaluation of the influence on safety

Incidence of TEAEs by SOC, PT, Grade **pre-switch** vs. **post-switch**:

- TEAEs
- SAEs
- AESIs
- Fatal TEAEs
- G3 vs. G4 TEAEs

The exposure as defined in Section 8.9.2 will be determined for both the CMC2 and CMC4 material.

Evaluation of the influence on efficacy

Based on the investigator response assessment (INV) the following quantities will be summarized:

- Median time to censoring post-switch due to data cut-off (considering only censored patients; no Kaplan-Meier methodology)

-
- Median time to PFS event post-switch (considering only patients with PFS event; no Kaplan-Meier methodology)
 - Median follow-up time after the switch (applying the reverse Kaplan-Meier method)

Based on the investigator response assessment, a swimmers plot will be produced for the patients who switched from CMC2 to CMC4, indicating:

- The bar length will represent the time to event / censoring
- Point in time when the CMC switch happened
- Point in time when PR or CR were detected first
- Patients without PFS event who are censored due to data cut-off (arrow head on top of bar)
- Patients who experienced a PFS event, or patients who were censored due to other reasons than data cut-off (blunt bar end); patients who are treated despite progression will have a blunt end at the time the PD was detected

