SAP ADDENDUM	Subgroup analyses: 
 • Safety and efficacy in patients who discontinued LEN • Safety in patients who are treated with a reduced dose of LEN (incidence of TEAEs, duration of TEAEs) • Patients treated with different CMC batches (efficacy and safety are evaluated) • Efficacy by age category • OS by best response • Forest plots for various efficacy variables and 	Various subgroup analyses were added to obtain a clearer picture on the efficacy and safety of the drug combination in different subgroups.

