10.2.5 Main analysis

- The tumour assessments will be derived according to the IWG treatment response criteria for malignant lymphoma (Cheson et al., 2007), by an Independent Radiology/Clinical Review Committee (IRC). The review process will be defined in the IRC Charter.
- The distribution of PFS will be estimated using the Kaplan-Meier (K-M) method. The median PFS time along with 95% confidence intervals will be presented (Brookmeyer and Crowley 1982). 25th and 75th percentiles will be considered as well.
- The PFS probabilities at specific time points (1 month, 3 months, 6 months, 12 months, 18 months, 24 months, 30 months), and the associated 95% CIs (Greenwood formula) will be summarized.
- PFS events will be described according to the type of event (death, documented tumour progression).
- The reason for censoring will be tabulated.
- A plot of the Kaplan-Meier curve for PFS will be provided.
- The median follow-up time for PFS including a 95% confidence interval (Brookmeyer and Crowley 1982) will be calculated using the reverse Kaplan-Meier method.
- No formal hypothesis testing will be conducted.
- The main analysis will be conducted on the FAS for both the IRC and INV response assessment.

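### The batch-switch efficacy summary in SAP 16.5.3 uses event-only and censored-only medians, which follow the length of follow-up far more than the PFS hazard; Kaplan-Meier PFS from the switch should replace them

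*SAP*

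**What the plan says.** The change summary at the front of the SAP lists the batch analysis among the Addendum 1.0 subgroup analyses: "Patients treated with different CMC batches (efficacy and safety are evaluated". Section 16.5.3 counts patients treated with CMC2 only, CMC4 only, or both, and for those who switched it describes the time to switch.

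For efficacy it is restricted to investigator assessment ("Based on the investigator response assessment (INV) the following quantities will be summarized") and plans four outputs:

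- "Median time to censoring post-switch due to data cut-off (considering only censored patients; no Kaplan-Meier methodology"
- a median time from the switch to a PFS event, "considering only patients with PFS event; no Kaplan-Meier methodology"
- "Median follow-up time after the switch (applying the reverse Kaplan-Meier method"
- a figure: "a swimmers plot will be produced for the patients who switched from CMC2 to CMC4". It marks the switch, the first PR or CR, and whether each bar ends in an event, in censoring at data cut-off, or in censoring for another reason.

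No post-switch PFS curve, PFS rate or hazard ratio by batch is planned in this section or elsewhere. Patients on a single material are counted, but no efficacy result is planned for them. Safety has a pre-switch versus post-switch tabulation; efficacy has no comparator.

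Elsewhere the SAP treats PFS in the usual way. Section 10.2.5: "The distribution of PFS will be estimated using the Kaplan-Meier (K-M) method". Section 16.5.1, on patients who stopped lenalidomide, restarts the clock at discontinuation and applies Kaplan-Meier to PFS and OS.

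**The concern.** A median taken only over patients who had an event is conditional on the event falling inside the observation window. Patients still progression-free do not enter it, although they carry much of the information on whether the new material works. The companion median over censored patients is essentially a description of follow-up. Neither is an estimate of post-switch PFS.

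The numeric part of the efficacy evaluation would therefore look much the same across a wide range of true post-switch outcomes. A change in data cut-off would move it more than a moderate change in efficacy would. Section 16.5.3 gives no reason for leaving the method used elsewhere in the SAP.

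**Working it through.** **Inputs.** Section 16.5.3 states no number of switchers, post-switch follow-up, event count or target effect, so there is no planned figure to reproduce. From the documents: about 80 patients (SAP 5.3), and a primary analysis about 12 months after the last enrolment (SAP 5.4.2). Assumed: exponential post-switch PFS with true median M, hazard λ = ln 2 / M, and independent censoring.

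**Step 1. Fixed follow-up C.** The event-only median m solves 1 − exp(−λm) = ½[1 − exp(−λC)]. The censored-only median is C itself, whatever the hazard.

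Example with M = 24 and C = 12: λ = 0.0289; exp(−12λ) = 0.707; the event share is 0.293; half of that is 0.146; m = −ln(0.854)/0.0289 = 5.5 months.

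Same hazard (M = 24), follow-up varied:

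| Follow-up (months) | 3 | 6 | 12 | 24 |
|---|---|---|---|---|
| Event-only median | 1.5 | 2.9 | 5.5 | 10.0 |
| Censored-only median | 3 | 6 | 12 | 24 |

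Same follow-up (C = 12), hazard varied four-fold:

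| True median (months) | 48 | 24 | 12 |
|---|---|---|---|
| Event-only median | 5.7 | 5.5 | 5.0 |
| Censored-only median | 12 | 12 | 12 |
| Share with an event | 16% | 29% | 50% |

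Doubling the follow-up from 6 to 12 months nearly doubles the event-only median (2.9 to 5.5). Doubling the hazard (M from 24 to 12) lowers it by half a month.

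**Step 2. Follow-up uniform over 6 to 18 months.** The chance of still being under observation, G(t), is 1 up to 6 months and (18 − t)/12 after that. The event-only median is the point that halves the integral of λ·exp(−λt)·G(t) over 0 to 18 months. True PFS at 12 months is exp(−12λ).

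| True median (months) | 3 | 6 | 12 | 24 | 36 |
|---|---|---|---|---|---|
| Event-only median | 2.6 | 3.9 | 4.9 | 5.4 | 5.6 |
| True 12-month PFS | 6% | 25% | 50% | 71% | 79% |

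Between true medians of 12 and 36 months, 12-month PFS differs by 29 percentage points and the event-only median by 0.7 months. The censored-only median over that range is 11.0, 11.5 and 11.7 months.

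**Step 3. What a proper comparison could achieve.** In 1,500 simulated data sets per hazard ratio (40 versus 40 patients, follow-up uniform over 2 to 12 months, reference median 24 months), a rank test on event-only times rejected in 4%, 6% and 5% of runs at hazard ratios 1, 2 and 3. A log-rank test on all patients rejected in 5%, 30% and 73%. By Schoenfeld's formula, 80% power at a hazard ratio of 2 with equal groups needs 4(1.96 + 0.84)²/(ln 2)² ≈ 66 events. In a trial of about 80 patients, even a correct comparison would find only large batch effects.

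**The case against.** The strongest defence is that the medians are only part of the section. The swimmers plot shows every switcher, including those event-free at cut-off, and a run of early progressions after the switch would be visible. Reverse Kaplan-Meier follow-up is also reported, so the dependence on follow-up is not hidden. This stands as context. The plot gives no estimate or interval, and the follow-up median measures observation time.

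A reader might infer that the event-only median cannot detect a batch effect, or that good and poor material give the same number. That goes too far. In Step 2 a true median of 3 months gives 2.6, and with a fixed 24 months of follow-up a doubled hazard (M from 24 to 12) moves it from 10.0 to 8.1. It is insensitive to moderate effects, not blind. Nor does the section as a whole ignore progression-free patients: one bullet does, while the other bullets and the plot cover them.

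A reader might also infer that the sponsor will claim batch comparability from these medians, or that the trial's efficacy result is in doubt. The documents support neither. Section 16.5.3 states no hypothesis, threshold or equivalence claim, and nothing in it feeds the primary ORR analysis or the main PFS analysis.

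**Conclusion.** The point holds as a defect in a secondary, descriptive analysis. Under a heading that promises an evaluation of efficacy, the SAP gives no estimate of post-switch PFS and offers two medians governed mainly by follow-up. For true median PFS from 12 to 36 months, the event-only figure stays between 4.9 and 5.6 months. These sizes rest on exponential PFS and an assumed 6 to 18 months of post-switch follow-up; other windows change the values, but the event-only median still responds more to follow-up than to moderate changes in hazard. The change should be made because it is cheap and brings the section into line with SAP 10.2.5 and 16.5.1.

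**What to change.** In SAP 16.5.3, replace the two medians with Kaplan-Meier PFS in switchers. Time zero is the first CMC4 dose, censoring follows Table 13, and the output gives numbers at risk and 6- and 12-month rates with 95% confidence intervals. State that patients whose progression preceded the switch are not at risk. Keep the reverse Kaplan-Meier follow-up and the swimmers plot. The switch dates are already needed for the time-to-switch histogram and the plot, so the cost is one extra table.

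Do not add a before-versus-after event rate within switchers. Patients generally had to remain on treatment without progression to reach the switch, so pre-switch events would be close to zero by construction (immortal-time bias).

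If a batch comparison is wanted, make it an optional exploratory Cox model with batch as a time-dependent covariate, including the CMC2-only and CMC4-only patients. Report it with its confidence interval, and state that precision is limited and that batch is confounded with time on treatment, including the planned end of lenalidomide after Cycle 12. This model is work beyond the one table.

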16.5.4 Efficacy by age category

Based on the FAS, PFS, OS, ORR, and DoR will be derived for the following subgroups as detailed in the respective SAP sections for both the INV and IRC response assessment. For time-to-event endpoints both Figures and Tables will be produced. The following categories are considered:

- Patients ≤ 70 years of age
- Patients > 70 years of age

16.5.5 Time to event analyses by best response category

OS will be summarized for the following categories based on the FAS:

- Patients having a CR as best response (as determined by IRC)
- Patients having a PR as best response (as determined by IRC)

A Kaplan-Meier curve for the two subgroups will be produced.

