4. STUDY OBJECTIVES AND ENDPOINTS

An overview of the study objectives and endpoints is depicted in Table 1.

Table 1: Study objectives and endpoints

Study objective	Endpoint	Analysis
Primary objective:	Primary endpoint:	
To determine the activity of a combination of LEN with MOR00208 in terms of objective response rate (ORR = complete response (CR) + partial response (PR)) in adult patients with R-R DLBCL	Best Objective Response Rate (ORR), defined as the proportion of responders whose best response at any time throughout treatment or follow-up is complete or partial (ORR=CR+PR)	See section 9
Secondary objectives:	Secondary endpoints:	
1. To determine the disease control rate (DCR = CR + PR + stable disease (SD) as best response)	Disease Control Rate (DCR = CR+PR+SD as best response)	See section 10.1
2. To determine progression-free survival (PFS)	Progression-free Survival (PFS)	See section 10.2
3. To determine the duration of response (DoR)	Duration of Response (DoR)	See section 10.3
4. To determine the overall survival (OS)	Overall Survival (OS)	See section 10.4
5. To determine time to progression (TTP)	TTP	See section 10.5

STATISTICAL ANALYSIS PLAN

 MorphoSys AG
 MOR208C203

6. To determine the time to next treatment (TTNT)	To determine the time to next treatment (TTNT)	See section 10.6
7. To determine the safety of LEN combined with MOR00208 assessed according to the frequency and severity of adverse events (AEs)	Incidence, frequency and severity of treatment-emergent AEs	See section 10.7
8. To assess the potential immunogenicity of MOR00208 (anti-MOR00208 antibodies)	Anti-MOR00208 antibody formation (ADA): number and percentage of patients who develop anti-MOR00208 antibodies; Titer determination; Characterization of ADA-positive samples (neutralizing vs non-neutralizing)	See section 10.8
9. To assess the pharmacokinetics (PK) of MOR00208	Summary statistics for PK: plasma concentration-time profiles of MOR00208 and appropriate individual PK parameters (e.g. accumulation ratios).	See section 10.9

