6.9 Start and end date for time to event variables

Assessment date

For each assessment (i.e. evaluation number), the **assessment date** is calculated as the latest of all measurement dates (e.g. X-ray, CT-scan) if the overall response at that assessment is CR/PR/SD/UNK/NE.

Otherwise - if overall response is progression – the assessment date is calculated as the earliest date of all measurement dates at that evaluation number.

Start dates

For all “time to event” variables, other than duration of response, the start date of study treatment will be used as the start date.

For the calculation of duration of response the following start date should be used:

Date of first documented response is the assessment date of the first overall response of CR or PR.

End dates

The end dates which are used to calculate ‘time to event’ variables are defined as follows:

- Date of death (during treatment as recorded on the treatment completion page or during follow-up as recorded on the study evaluation completion page or the survival follow-up page).
- Date of progression is the first assessment date at which the overall response was recorded as progressive disease.
- When there is no documentation of radiologic evidence of progression, and the patient discontinued for ‘Disease progression’ due to documented clinical deterioration of disease, the date of discontinuation is used as date of progression.
- If no post-baseline assessments are available (before an event or a censoring reason occurred) the start date of study treatment is used as the end date.

Calculation of ‘time to event’ variables

Time to event = End Date - Start date + 1 (in days).

When no post-baseline tumor assessments are available, the start date of study treatment will be used as end date (duration = 1 day).

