9.1 Endpoint: Best objective response rate

The best ORR is defined as the proportion of patients with CR or PR as best response achieved at any time during the study. The denominator will be the total number of patients included in the analysis population.

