10.2.3 Disease assessments

Disease assessments will be performed with either PET/CT scans or CT/MRI scans as per the schedule in Table 12.

STATISTICAL ANALYSIS PLAN

 MorphoSys AG
 MOR208C203

Table 12: Schedule of Tumour Assessments

Evaluation	Screening	C3 D1	C5 D1	C7 D1	C10 D1	C12 D28	C13 D1	Every 3 months	From C25 D1 onward once per year	EOT visit
Disease response assessment (PET/CT or PET/MRI)	X					X			X [§]	X
CT or MRI scan for tumour measurement and disease response assessment		X	X	X	X		X*	X	X	

*Can be done approx. 3 months after C12D28 PET/CT or PET/MRI assessment.

§Only if deemed necessary and not more frequently than once per year. A window of ± 2 weeks is allowed by the protocol for these assessments. Tumour assessments will continue until disease progression, death or study discontinuation (whichever occurs first).

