10.4.2 Endpoint: Overall survival

Overall survival (OS) is defined as the time from the date of the first administration of any study drug until death from any cause (documented by the date of death).

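### Overall survival curves by best response (CR versus PR) run from first dose with no landmark, so they tend to separate in favour of CR even if CR has no effect on survival

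*SAP*

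**What the plan says.** SAP Section 16.5.5, part of Addendum 1.0, states that "OS will be summarized for the following categories based on the FAS". It defines two groups by best IRC response, CR and PR, and plans that "A Kaplan-Meier curve for the two subgroups will be produced". It names no test, hazard ratio, landmark or time-dependent covariate.

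The clock and the grouping variable are defined elsewhere:

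- **Time zero.** Section 10.4.2: "Overall survival (OS) is defined as the time from the date of the first administration of any study drug until death from any cause". Section 6.9 says the same for every time-to-event variable except duration of response: "the start date of study treatment will be used as the start date".
- **Window for best response.** Section 9.1 uses the "proportion of patients with CR or PR as best response achieved at any time during the study". Table 1 in Section 4 is equally open, covering treatment and follow-up.
- **Scan schedule.** Table 12 in Section 10.2.3 has CT or MRI at C3D1, C5D1, C7D1 and C10D1. For a patient who stays on treatment, the first scheduled post-baseline PET/CT is at C12D28.

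**The concern.** Patients are sorted by something that happens after time zero but are followed from time zero. Both groups are guaranteed to live until their first response. A patient who converts from PR to CR is also guaranteed to live from the PR to the CR, and the curve gives that interval to CR. A PR patient who progresses or dies early never gets the chance to convert and stays in the PR group.

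Three features of the plan make this more than theoretical:

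- The response criteria (Protocol Appendix G; SAP Table 3) accept a residual mass as CR in PET-positive disease only if it becomes PET negative, and eligibility requires a PET-positive lesion. With scheduled PET/CT at C12D28, some conversions may be recorded only after about 11 months, unless an end-of-treatment or optional PET (Protocol 7.2.14.1) comes earlier.
- The note to the alternative censoring table in SAP 20.9 says that PFS follow-up stops with treatment. Patients who stop early therefore largely lose the opportunity to be recorded as CR.
- SAP 20.5.3 counts transitions from PR to CR, so late conversion is expected.

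At stake is the reading of the figure. Two curves by depth of response invite the conclusion that CR prolongs survival, and part or all of the visible gap could be guarantee time.

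**Working it through.** The plan gives no sample size, event count or effect for this analysis, so there is no figure to reproduce. The check has two parts: the timing implied by the schedule, and a simulation in which CR has no effect on progression or death.

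**Timing (28-day cycles).** C3D1 = 2 × 28 + 1 = day 57. C7D1 = 6 × 28 + 1 = day 169. C12D28 = 12 × 28 = day 336, and 336 / 30.4375 = 11.0 months.

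**Null model.** The rates are assumptions and are not in the documents. All responders are progression-free at day 57. Time to progression (TTP) and post-progression survival are exponential and do not depend on response. A PR becomes CR only at a scheduled scan while progression-free. OS runs from first dose with a 36-month cut-off. The hazard ratio (HR), CR versus PR, is the one-step log-rank estimate exp[(O − E)/V].

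The fifth column of the table is (final CR share − first-scan CR share) / (1 − first-scan CR share).

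| Median TTP (months) | Median post-progression survival (months) | CR at first scan | Conversion per later scan | First-scan PRs that convert | Null HR as planned | 24-month OS, CR vs PR |
|---|---|---|---|---|---|---|
| 6 | 10 | 20% | 15% | (0.46 − 0.20)/0.80 = 33% | 0.68 | 51% vs 35% |
| 12 | 12 | 20% | 15% | (0.57 − 0.20)/0.80 = 46% | 0.54 | 72% vs 51% |
| 12 | 12 | 40% | 10% | (0.61 − 0.40)/0.60 = 35% | 0.68 | 69% vs 55% |
| 24 | 12 | 20% | 15% | (0.66 − 0.20)/0.80 = 58% | 0.43 | 84% vs 64% |
| 24 | 12 | 40% | 5% | (0.55 − 0.40)/0.60 = 25% | 0.76 | 81% vs 74% |

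The true HR is 1 in every row. A second simulation under the same kind of null, also over five assumed scenarios, gave 0.27 to 0.74. The upper ends agree and the lower end depends on the model, so about 0.3 to 0.75 is a fair summary.

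The only document figure for later improvement is the 25% of SD or PR patients in the cited lenalidomide monotherapy study (Protocol 1.3.1). It covers any improvement in a different population. The scenario with the same overall conversion, the last row, has the smallest bias.

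**Does a landmark remove it?** Groups are fixed by response up to the landmark, and OS is measured from there.

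- Patients alive at the landmark: null HR 0.90 to 0.98 at C7D1 and 0.80 to 0.95 at C12D28. Bias remains because patients who have progressed are still alive, cannot convert, stay in the PR group and die sooner.
- Patients alive and progression-free: null HR 0.99 to 1.01 at both landmarks.

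**What the landmark costs.** With exponential TTP, the share of responders lost is 1 − 2^(−d/m), where d is the months from day 57 to the landmark and m is the median TTP.

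- C7D1: d = (169 − 57)/30.4375 = 3.68. Loss is 35% at m = 6 and 10% at m = 24.
- C12D28: d = (336 − 57)/30.4375 = 9.17. Loss is 65% at m = 6 and 23% at m = 24.

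At the planned ORR there are 0.35 × 80 = 28 responders. That leaves about 18 to 25 at C7D1 and 10 to 22 at C12D28, before splitting into two groups.

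**The case against.** The strongest reply is that nothing is being compared. Section 16.5.5 summarises and plots. Where the SAP wants a contrast it says so: log-rank tests and Cox hazard ratios in 10.12.3, Cox hazard ratios in 10.10.2 and 11.4, and forest plots in 16.5.6 restricted to the subgroups of 10.10, 10.12 and 11.4. Section 10.4.4 rules out formal hypothesis testing for OS. This stands. A reader might infer that the SAP tests whether CR improves survival, or claims that it does; the text supports neither. What remains is that the figure sets the two curves side by side and carries no caution.

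It can also be said that the plan shows response timing elsewhere, through time to CR (11.1) and the swimmers plot of responders (16.5.9). Those outputs help a careful reader but do not correct the OS curves.

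Third, the size is not documented. That also stands. A reader might want to quote one pair of medians as the bias, but TTP, early CR rate and conversion rate are all assumed, and only a range is defensible.

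Finally, the unbiased landmark discards responders from a small set. This is a real cost. It bears on which landmark to prefer and does not rescue the unadjusted display.

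**Conclusion.** The point holds for a descriptive, supportive display. From the definitions in the SAP, OS by best response in Section 16.5.5 contains guarantee time that favours CR, and nothing in the plan removes it. With no true effect, the apparent HR is about 0.3 to 0.75 under the stated assumptions. The direction was the same in every scenario; the size depends mainly on how many patients convert and how late.

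It would go too far to say that the whole of any observed gap is artefact, since CR may have a real association with survival that these curves cannot isolate. It would also go too far to extend the point to the primary ORR or to the main OS analysis, neither of which groups patients by response for survival.

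**What to change.** Add to Section 16.5.5, or substitute for the present curves, OS measured from a fixed landmark: C7D1 as main, C12D28 as sensitivity. Include responders who are alive and progression-free by IRC at the landmark, and group them by best IRC response up to that date. Requiring only that patients be alive is not enough. State how responders are handled whose IRC follow-up ended before the landmark without progression, because PFS follow-up stops with treatment. A Cox model with CR as a time-dependent covariate that accounts for progression is an optional support.

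If the unadjusted curves are kept, add a footnote that they are descriptive, subject to guarantee-time bias and not evidence that CR prolongs OS.

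The cost is one derivation from dates already collected. The downside is the exclusion of responders who progressed or died before the landmark (under the assumptions above about 10 to 35% at C7D1 and 23 to 65% at C12D28) and of those who first respond after it. The C12D28 set may be small, which is why C7D1 is the better main choice. The SAP already resets time zero for another post-baseline grouping, lenalidomide discontinuation in Section 16.5.1, so the approach is not foreign to the plan.
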